2.4.2 Data Monitoring Board

An independent Data and Safety Monitoring Board (DSMB) will be assembled to review safety, tolerability and efficacy (as needed) data collected on volanesorsen during this study. Based on its ongoing assessment of the safety and tolerability of volanesorsen, the DSMB will provide recommendations to the Sponsor for modifying, stopping or continuing the study as planned. Details on the safety assessments, frequency of review, meeting schedules and controlled access to unblinded data are outlined in the DSMB Charter.

In order to ensure maintenance of the study blind before index study completion, lipid panel results, including apoC-III, will not be available to the Sponsor, monitors, Investigators, Study Center personnel, or the patients, except for the procedure related to safety monitoring for LDL-C elevations as specified in protocol section 8.5.5.

For the purpose of pre-programming and data cleaning, PAREXEL unblind programming team (the CRO performing the statistical analysis) and an independent data manager at Medpace Laboratories will receive post-baseline lipid panel results.

2.5 Data Management

The following is applied to all index studies (ISIS 304801-CS6 or ISIS 304801-CS16) and all 3 groups in this open-label study.

2.5.1 Case Report Form (CRF) Data

BioClinica® is responsible for creating the Electronic Data Capture (EDC) data entry screens, database and edit checks using definitions developed by the Sponsor. The Sponsor is responsible for the review, data management querying and locking of the database.

Data are single-entered into the EDC system by the investigator site staff. Programmed edit checks (computer logic that checks the validity of the data entered and also prompts for missing data that is expected to be entered) are run and automatic queries are generated. The Sponsor performs blinded review of all data for accuracy and validity; generating additional queries in the EDC system when necessary. The data is corrected or an explanation concerning the query is provided in the EDC system. After all data is entered, reviewed, source data verified and all queries are resolved the database will be locked.

2.5.2 *Laboratory Data*

The Sponsor is responsible for the format of the laboratory electronic data transfers and the transfer schedule. The Sponsor is responsible for the review of the clinical laboratory data. This data is not stored in the EDC system. Investigator sites have access to the data via printed lab reports sent directly from the laboratory.

2.5.3 *Pharmacokinetics (PK) Data*

The Sponsor is responsible for the management and review of the PK data. This process involves reviewing the patient and visit identifiers with the clinical data collected in the EDC system. The PK data are not stored in the EDC system.

2.5.4 *Other Data*

Bracket is the eDiary vendor that contains abdominal pain and QoL assessments. Medpace Imaging Central Lab manages MRI, ECHO, and Fundus photography. Blood Center of Wisconsin manages antiplatelet antibodies and anti-PF4 assay data. Quest Pharmaceutical Service manages anti-volanesorsen antibody assessment. University of Western Ontario (████████ Professor ██████████) manages genetic sequencing data. These data will also not be stored in the EDC system but will be transferred to the Sponsor as external data.

2.5.5 *Adverse Events Adjudication*

████████ is the vendor that manages the adjudication process.

All SAEs that occur during the study that are consistent with MACE will be adjudicated by a blinded, independent committee as outlined in the MACE Adjudication Charter.

All AEs and SAEs that occur during the study that are consistent with an event of acute pancreatitis will be adjudicated by a blinded, independent committee according to the Atlanta classification of acute pancreatitis (Banks et al. 2013) and as outlined in the Pancreatitis Adjudication Charter. In addition, data for prior episodes of acute pancreatitis or suspected pancreatitis will be collected by review of each patient's medical chart and these events will also be independently adjudicated.

3 ANALYSIS PLAN

3.1 Statistical Design Summary

This is a multi-center open-label study of:

Group 1: ISIS 304801-CS6 (index study) roll over FCS patients

Group 2: ISIS 304801-CS16 (index study) roll over FCS patients

Group 3: FCS patients who did not participate in the ISIS 304801-CS6 or ISIS 304801-CS16 index studies.

Group 1 and Group 2 patients who complete one of the index studies and who are qualified plus Group 3 patients who are screened and qualified will be enrolled to this open-label study. The safety and efficacy of extended dosing with volanesorsen in patients with FCS will be evaluated by summary tables rather than hypothesis tests. Missing data will not be imputed.

3.1.2 *Sample Size Consideration*

No sample size calculations were performed as this is an open-label extension study.

3.1.3 *Planned Interim Analysis*

An interim analysis may be conducted after the last patient's Week 13 visit of the open-label study or after the database of the ISIS 304801-CS6 and ISIS 304801-CS16 index studies are locked and unblinded.

Planned summaries and patient data listings for disposition, demographic, efficacy and safety will be included in this interim analysis.

Additional interim analyses will be performed to support regulatory filing activities.

3.2 General Overview of Analyses

3.2.1 *Statistical Methods*

All eCRF data, lab data transfers, as well as any outcomes derived from the data, will be provided in the patient data listings. Patient data listings will be presented for all patients enrolled into the study. Descriptive summary statistics including n, mean, median, standard deviation, standard error, interquartile range (25th percentile, 75th percentile), and range (minimum, maximum) for continuous variables, and counts and percentages for categorical variables.

Efficacy data including fasting lipid measurements, abdominal pain and QOL results will be mapped to analysis visit specified in the table below.

The intent of these visit windows is not to align with those prescribed for visit scheduling in the clinical study protocol but, rather, based on the protocol-defined target study day, to delineate mutually exclusive windows so that all efficacy assessments proximal to a particular study week can

be integrated to best represent the patient's status during that period of the study. If a patient discontinued early from the treatment period but attended applicable landmark visits at Weeks 12, 13, 25 and etc. to collect efficacy assessments, then those assessments collected at Early Termination visit and during post-treatment follow-up period should be mapped to analysis visits as well. If there are multiple assessments within a visit window, only scheduled visit will be used. If there are multiple scheduled assessments, for fasting lipid measurements and numeric QOL results, average will be used; for abdominal pain and character QOL results, the worst will be used. If the assessments are all unscheduled, the visit nearest the scheduled date will be used unless two visits are equally near, in which case the average will be used. For fasting lipid data, local lab data will not be used unless central lab assessments are not available at certain visit. When calculating the baseline and analysis endpoints, only if the data from central lab is missing, then the local lab data will be utilized.

Efficacy/PD measure	Mapped Visit (Week)	Target	Study Day Window
Fasting Lipid Assessment	Screening	-56 to -15	≤ -15
	Qual Visit	-14 to -7	-14 to <1
	1	1	1
	4	22	2 to 36
	8	50	37 to 64
	12	78	65 to 82
	13	85	83 to 106
	25	169	107 to 173
	26	176	174 to 197
	38	260	198 to 302
	50	344	303 to 351
	52	358	352 to 400
	extended treatment period		
	64	442	401 to 484
	76	526	485 to 575
	90	624	576 to 673
	104	722	674 to 743
	117	813	744 to 858
	130 (France)	904	859 to 949
Abdominal Pain			
	m	$n \times 7 + 1$	$mx7+3 \text{ to } mx7-3,$ $m = -1, -2, \dots$
	...		
	-2	-13	-11 to -17
	-1	-6	-4 to -10
	1	1	1 to -3
	2	8	5 to 11

	3	15	12 to 18
	n	(n-1) × 7+1	(n-1) × 7-2 to (n-1) × 7+4
	...		
MRI			
	Screening	NA	≤ 14
	52	358	298 to 418
Quality of Life Assessments (EQ-5D, SF-36)			
	1	1	1
	13	85	55 to 115
	26	176	146 to 206
	52	358	328 to 404
	65	449	405 to 479
	78 (France)	540	496 to 570
	117 (France)	813	769 to 843
	130 (France)	904	860 to 934

Note: Regarding lipid measurements for efficacy analyses, mapped observed assessments defined in this table will be derived further. The derivations for baselines are described in [section 3.2.3](#). The derivations for Month 3, 6 and 12 are described in [section 3.3.1](#).

Non-efficacy by visit assessments will be summarized using the visit labels provided in the data. Multiple results with the same visit label will be averaged.

Unscheduled results and data from local labs will not be included in the by visit summaries but will be used in the determination of baseline, in the laboratory abnormality, stopping rule, and platelets reduction analyses presented in data listings.

Unscheduled results from the central lab will be used in the determination of baseline, laboratory abnormality summaries, and shift from **safety baseline** to worst post-baseline, and platelets reduction analyses only, and presented in data listings. Local lab data will be only used in platelet analyses (including by visit summaries, abnormality summary, shift from Baseline to worst post-baseline, reduction analyses), and presented in data listings.

Summary tables and figures will NOT be presented by the treatment group in each index study (ISIS 304801-CS6 or ISIS 304801-CS16) and the newly enrolled patients as a separate group per protocol. Per Sponsor decision, most summary tables and figures will be presented in the following groups, i.e. Treatment naive group, CS6-Volanesorsen, CS16-Volanesorsen, and Overall, if applicable.

Note: “Treatment naive group” for most tables and figures is a combined group of subjects including CS7-New, CS6-Placebo and CS16-Placebo. When the summary is based on **Index Study Baseline**, “Treatment naive group” is a combined group of subjects including CS6-Placebo and CS16-Placebo.

Summary tables for PK concentration and IM data will be presented by Treatment naive group, CS6-Volanesorsen, CS16-Volanesorsen, and Volanesorsen combined (i.e., CS6-Volanesorsen and CS16-Volanesorsen combined). Summary figures for PK concentration data and summary tables for PK parameters will be presented by Treatment naive group and Volanesorsen combined.

Total patient year of exposure will be calculated as summation of [minimum (latest visit date, data cutoff date) – treatment start date +1]/365.25 for all subjects.

For listings, data will be displayed as an order of following:

- Treatment naive group: CS7-New
- Treatment naive group: CS6-Placebo
- Treatment naive group: CS16-Placebo
- CS6-Volanesorsen
- CS16-Volanesorsen

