Any patient who discontinues early from the Treatment Period should be followed as per the platelet monitoring rules shown in Section 8.6.3 of the protocol for the first 6 weeks after discontinuing Study Drug. Following this period, if the platelet count is stable (at least 3 consecutive values that are stable as determined by the Sponsor Medical Monitor and $> 100,000/\text{mm}^3$), the next platelet count should be taken within at least 6 weeks so that patients are monitored for at least 12 weeks after discontinuing Study Drug. Patients should also be strongly encouraged to attend applicable landmark visits at Weeks 12, 13, 25, 26, and 50, 52 (calculated based on the time elapsed since Day 1) to collect fasting lipid panels and conduct safety assessments in accordance with the Schedule of Procedures. Any patient who discontinues treatment after Week 44 should also be strongly encouraged to attend a final follow-up visit (Week 65 visit assessments) approximately 13 weeks after their last dose of Study Drug, in addition to the applicable landmark visits.

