Participation in the PK subgroup is optional for sites and patients, and consent may be withdrawn for the subgroup-specific procedures (e.g., multiple blood draws for PK) without being withdrawn from the study. If a patient withdraws consent from the subgroup procedures, he/she should remain on study and continue to follow all the non-subgroup assessments and procedures as outlined in Appendix A of the protocol.

2.1.5 *Post-Treatment Period*

After completion of the Week 52 visit assessments, patients will have the option of participating in an expanded access program or continuing dosing for up to an additional 52 weeks until an expanded access program is approved and available in their country. Patients not participating in an expanded access program will enter the 13-week post-treatment evaluation period. This 13-week post-treatment evaluation period consists of 4 Study Center visits on Weeks 54, 56, and 58 (which may be conducted by a home healthcare nurse), and Week 65 as outlined in the Schedule of Procedures in Appendix A of the protocol. Patients who complete, or terminate early from, the extended treatment period without subsequently participating in an expanded access program will enter a 13-week post-treatment evaluation period consisting of 4 Study Center visits on Weeks 106, 108, and 110 (which may be conducted by a home healthcare nurse), and Week 117 as outlined in the Schedule of Procedures in Appendix A of the protocol.

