3.3 Efficacy Analysis

Efficacy endpoints include: percent change and change in fasting lipid measurements, frequency and severity of patient reported abdominal pain, change from baseline in QOL, adjudicated acute pancreatitis events rate and frequency of other symptoms.

Efficacy analyses will be conducted in the FAS by the group presented in [Section 3.2.1](#).

For fasting lipid measurements and QOL (EQ-5D, SF-36), both the **Index Study Baseline** and the **Open-label Study Baseline** will be used. In the summary tables using the **Open-label Study Baseline**, visits are mapped to analysis visits as shown in [Section 3.2.1](#) for fasting lipid measurements and QOL (EQ-5D, SF-36) in the open-label study. In the summary tables using the **Index Study Baseline**, visits include the index study baseline visit, and the open-label study mapped post baseline visits.

Efficacy analyses for the fasting TG will be performed on FAS.

By patient listings will have all efficacy endpoints results collected in the open-label study.

Summary table and by patient listing will be generated by visit window, dose level, fasting TG and corresponding change from baseline value, nadir platelet, any pre-treatment adjudicated pancreatitis events, and abdominal pain event (average of intensity and yearly rate of frequency of moderate or severe events). Below visit windows will be utilized:

Visit Window	Dose Level	TG	Platelet Nadir	Abdominal Pain
0-3 months	week 1-13	month 3	day 1-91	week 2-14
3-6 months	week 14-26	month 6	day 92-182	week 15-27
6-9 months	week 27-39	week 38	day 183-273	week 28-40
9-12 months	week 40-52	month 12	day 274-364	week 41-53
12-15 months	week 53-65	week 64	day 365-455	week 54-66
15-18 months	week 66-78	week 76	day 456-546	week 67-79
18-21 months	week 79-91	week 90	day 547-637	week 80-92
21-24 months	week 92-104	week 104	day 638-728	week 93-105
24-27 months	week 105-117	week 117	day 729-819	week 106-118

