3.3.2 Percent change and absolute change from baseline in fasting TG

The Month 3 analysis time point is at the end of Month 3 where the value is defined as the average of Week 12 (Day 78) and Week 13 (Day 85) fasting assessments. If one visit is missing, then the other visit will be used as the 3-month endpoint. If both visits are missing, then the 3-month endpoint will be set as missing.

The Month 6 analysis time point is at the end of Month 6 where the value is defined as the average of Week 25 (Day 169) and Week 26 (Day 176) fasting assessments. If one visit is missing, then the other visit will be used as the 6-month endpoint. If both visits are missing, then the 6-month endpoint will be set as missing.

The Month 12 analysis time point is at the end of Month 12 where the value defined as the average of Week 50 (Day 344) and Week 52 (Day 358) fasting assessments. If one visit is missing, then the other visit will be used as the 12-month endpoint. If both visits are missing, then the 12-month endpoint will be set as missing.

Percent change and absolute change from the **Open-label Study Baseline** at Month 3, Month 6, and Month 12 in this open label study, and percent change and absolute change from the **Index Study Baseline** in fasting TG at index study Month 3, Month 6, and Month 12, and the open label study Month 3, Month 6, and Month 12 will be summarized. For patients enrolled to extended treatment period, percent change and absolute change from the **Open-label Study Baseline** and percent change and absolute change from the **Index Study Baseline** in fasting TG at Week 64, 76, 90, and 104 will also be summarized.

These analyses will be repeated using on-treatment period data, which is defined as the last dose date of study medication + 28 days.

A descriptive summary of TG over time will be conducted overall and by age group (<65 years vs. ≥ 65 years). A descriptive summary of TG over time during on-treatment period will also be conducted overall.

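### Lipids are mapped by study day whether or not the patient is still dosed, but only TG gets an on-treatment repeat; apoC-III and seven other lipids get none

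*SAP*

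**What the plan says.** **Mapping.** Section 3.2.1 says "Efficacy data including fasting lipid measurements, abdominal pain and QOL results will be mapped to analysis visit specified in the table below". Its stated purpose is to "delineate mutually exclusive windows so that all efficacy assessments proximal to a particular study week can" be pooled to describe the patient at that time. The same paragraph sends Early Termination and post-treatment follow-up results of early discontinuers into the same windows. No row asks whether the patient is still being dosed.

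**Return visits.** Section 2.1.2 strongly encourages patients who stop early to attend "applicable landmark visits at Weeks 12, 13, 25, 26, and 50, 52 (calculated based on the time elapsed since Day 1"), and fasting lipid panels are collected there.

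**Population.** Section 3.3 states "Efficacy analyses will be conducted in the FAS by the group presented in" Section 3.2.1.

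**TG.** Section 3.3.2 adds "These analyses will be repeated using on-treatment period data", with the limit set at last dose + 28 days. It also says "A descriptive summary of TG over time during on-treatment period will also be conducted overall".

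**The other eight measures.** Sections 3.3.6 (total cholesterol, non-HDL-C, apoB, HDL-C, apoA-1, VLDL-C, LDL-C) and 3.3.7 (apoC-III) plan the same kind of change analyses and over-time summaries. Neither mentions on-treatment data. In both, the sentence on Weeks 64, 76, 90 and 104 names fasting TG instead of the section's own measures.

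**Extension.** Section 3.3.2 reads "For patients enrolled to extended treatment period, percent change and absolute change from the" two baselines, summarized at Weeks 64, 76, 90 and 104. Under Section 2.1.5, completers and those who "terminate early from, the extended treatment period without subsequently participating in an expanded access program will enter a 13-week post-treatment evaluation period".

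**The concern.** Mapping results whether or not the patient is on drug describes what happens to everyone who started. It does not describe the effect while dosed. The sponsor evidently wanted both views for TG and planned both. For apoC-III, the target of the drug, and for seven other listed efficacy measures, only the first view exists.

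If one of these measures shows a smaller change at a later time point, a reader of the tables cannot tell a fading effect on drug from patients having stopped. The study's objective concerns extended dosing, and Section 3.1 says it will be evaluated by summary tables, so what sits in those rows is the evidence. No test, error rate or sample size is involved.

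**Working it through.** **1. Sections side by side**

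| Measures | Section | Change analyses | Over-time summary | On-treatment repeat |
|---|---|---|---|---|
| TG (1) | 3.3.2 | yes | yes | yes: change analyses and overall over-time summary |
| Other lipids (7) | 3.3.6 | yes | yes | none |
| apoC-III (1) | 3.3.7 | yes | yes | none |

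With a repeat: 1 of 9. Without: 7 + 1 = 8 of 9.

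**2. Landmark visits to Week 52**

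Day = 7 × (week − 1) + 1. This reproduces the SAP's target days: Weeks 12, 13, 25, 26, 50 and 52 give Days 78, 85, 169, 176, 344 and 358. By the TG rule a sample is on treatment if its day is no later than last-dose day + 28. The earliest last dose that keeps a landmark sample on treatment is therefore landmark day − 28:

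| Landmark | Day | Day − 28 | Last-dose week |
|---|---|---|---|
| Week 12 | 78 | 50 | 8 |
| Week 13 | 85 | 57 | 9 |
| Week 25 | 169 | 141 | 21 |
| Week 26 | 176 | 148 | 22 |
| Week 50 | 344 | 316 | 46 |
| Week 52 | 358 | 330 | 48 |

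A patient who stopped before the week shown and returns as asked gives an off-treatment value. Illustration: last dose at Week 20 (Day 134), on-treatment limit Day 162.

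- Month 6 averages samples at 169 − 134 = 35 and 176 − 134 = 42 days after the last dose.
- Month 12 averages samples at 344 − 134 = 210 and 358 − 134 = 224 days after the last dose.

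All four lie beyond + 28 days. They would leave the TG on-treatment tables but stay in the only tables planned for the other eight measures.

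**3. Extension rows (conditional)**

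The windows are Week 64: 401–484; Week 76: 485–575; Week 90: 576–673; Week 104: 674–743; Week 117: 744–858. Assume that an early stopper of the extension has a lipid sample at the end of the 13-week follow-up, at last dose + 91 days. For last-dose weeks 53 to 104:

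- Weeks 53–57 fall in the Week 64 row (5)
- Weeks 58–70 fall in the Week 76 row (13)
- Weeks 71–84 fall in the Week 90 row (14)
- Weeks 85–94 fall in the Week 104 row (10)
- Weeks 95–104 fall in the Week 117 row (10)

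That puts 5 + 13 + 14 + 10 = 42 of 52 last-dose weeks in a Week 64–104 row, each sample 91 − 28 = 63 days past the on-treatment limit. With the visit 7 days early or late (the window that Section 3.4.1.1 gives the Week 117 PK visit) the count is 43 or 41. These are calendar weeks, not patients.

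If the follow-up is instead held at the weeks Section 2.1.5 prints, only Week 106 (Day 736) falls in a Week 64–104 row, namely Week 104. Weeks 108, 110 and 117 (Days 750, 764 and 813) fall in the Week 117 row.

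**The case against.** The mapping is a declared choice, not an oversight. Section 3.2.1 states it openly and Section 3.2.2 calls the FAS the practical intent-to-treat population. That stands: the mapping is not itself an error. What is missing is its on-treatment companion, which the sponsor thought worth having for TG.

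A reader might go further and infer that the Week 64–104 rows are in fact contaminated with off-drug values. The documents do not support that:

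- Section 2.1.3 names a lipid panel during extended treatment. Section 2.1.5 names none in follow-up and refers to a protocol schedule that is not shown.
- The lipid table has a Week 117 row without the France mark that Week 130 carries, which hints at a follow-up draw. But the TG table in Section 3.3 pairs Week 117 with dosing in Weeks 105–117, so that row may serve dosed patients.
- The + 91-day visit is an assumption. Section 2.1.2 uses about 13 weeks after the last dose for patients who stop after Week 44, which makes it plausible, but Section 2.1.5 prints Weeks 106 to 117.
- Patients who move to expanded access have no follow-up and add no off-drug value.

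A reader might also infer that patients leaving at Week 52 fill the Week 64 row, since Week 65 (Day 449) lies in 401–484 and lipids have no Week 65 row. This too is uncertain. The instruction to map follow-up data concerns early discontinuers, the change summaries are limited to patients in the extension, and a Week 65 lipid draw is not shown.

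Finally, the by-patient listings and the discontinuation-by-month table let a determined reader trace individual cases. They do not replace a summary.

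**Conclusion.** The point holds, at minor severity. Eight of nine fasting lipid measures have no on-treatment summary to set beside a mapping that deliberately includes off-drug results. For the Week 12 to 52 landmarks this follows from the SAP's own text. It needs only that some patients stop early and return as encouraged. For the Week 64 to 104 rows it holds only if lipids are drawn in post-treatment follow-up, and the 42 of 52 count applies only with a sample at last dose + 91 days.

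As worded, Sections 3.3.6 and 3.3.7 plan no Week 64–104 change summary of their own measures, which leaves the over-time summaries for those weeks. This is probably a copying slip, and correcting it alone would not close the gap: being enrolled in the extension is not the same as being on drug.

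The number of patients affected is not given, so no bias in any mean is claimed.

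**What to change.** 1. Add to Sections 3.3.6 and 3.3.7 the on-treatment repeat already written for TG in Section 3.3.2 (last dose + 28 days), covering both the change analyses and the over-time summaries.
2. In the Week 64, 76, 90 and 104 sentences of those two sections, replace fasting TG with the intended measures.
3. Optionally, show any post-treatment lipid samples taken after Week 52 in separate follow-up rows by days since last dose.

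The cost is SAP wording and a few extra descriptive tables. Item 3 also needs one derived variable, days since last dose. No new visits or data are required, and the existing all-data summaries stay as they are unless item 3 is adopted.

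### Fasting-lipid windows have no post-treatment row for patients who stop at Week 52, so a sample about 13 weeks off drug is labelled Week 64; two earlier windows send samples to the farther visit

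*SAP*

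**What the plan says.** The Section 3.2.1 window table gives fasting lipids these rows around the end of the main treatment period: Week 50 (Days 303-351), Week 52 (Days 352-400) and then, under an extended-treatment subheading, Week 64 (Days 401-484). Week 104 covers Days 674-743 and Week 117 covers Days 744-858. There is no lipid row for Week 65, although the QOL part of the same table has one.

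Section 2.1.5 says that patients who neither extend nor join expanded access have a follow-up that "consists of 4 Study Center visits on Weeks 54, 56, and 58 (which may be conducted by a home healthcare nurse), and Week 65". After the extended period the follow-up is described as "consisting of 4 Study Center visits on Weeks 106, 108, and 110", and Week 117.

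For several values in one window, Section 3.2.1 says: "If there are multiple scheduled assessments, for fasting lipid measurements and numeric QOL results, average will be used". A note under the table adds: "Regarding lipid measurements for efficacy analyses, mapped observed assessments defined in this table will be derived further". Month 12 is the mean of Week 50 and Week 52, or whichever of the two is available (Section 3.3.2).

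The sentence "those assessments collected at Early Termination visit and during post-treatment follow-up period should be mapped to analysis visits as well" applies to patients who stopped treatment early and attended landmark visits. No sentence says what happens to follow-up lipids from patients who completed treatment.

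Section 3.3.2 limits the later change summaries: "For patients enrolled to extended treatment period, percent change and absolute change from the" each baseline at Weeks 64 to 104. It repeats the TG change analyses, and the overall TG-over-time summary, on data up to last dose + 28 days. Sections 3.3.3 (response rates), 3.3.6 (other lipids) and 3.3.7 (apoC-III) state no such repeat.

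**The concern.** The trial's objective is the safety and efficacy of dosing and extended dosing. A reader of a lipid curve will take the Week 64 point as a value under continued treatment. If it includes patients who stopped at Week 52, part of any movement between Week 52 and Week 64 is washout and could be taken for loss of effect.

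The change log explains the width of the window: the Week 52 and Week 64 limits were set from the midpoint to the next visit. For a patient who stops at Week 52, the next lipid row, Week 64, is not a visit on that patient's schedule. The window therefore runs 42 days past the Week 52 target into follow-up.

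A smaller question arises earlier in the table. The Week 13 and Week 26 windows stop well short of the midpoint to the next row, so some samples are assigned to the more distant visit. Section 3.2.1 says that the windows are meant to gather assessments proximal to a given week.

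**Working it through.** **Target days.** Target = (week - 1) × 7 + 1. This reproduces the SAP's own figures: Week 52 = 358, Week 64 = 442, Week 76 = 526, Week 104 = 722, Week 117 = 813. It gives Week 65 = 449, as in the PK schedule in Section 3.4.1.1.

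**Window limits.** (358 + 442)/2 = 400 and (442 + 526)/2 = 484, exactly as stated.

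**Placing the post-treatment visits**

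| Visit | Day | Days after Week 52 or 104 target | Lipid window |
|---|---|---|---|
| Week 54 | 372 | 14 | Week 52 |
| Week 56 | 386 | 28 | Week 52 |
| Week 58 | 400 | 42 | Week 52 (last day) |
| Week 65 | 449 | 91 | Week 64 |
| Week 106 | 736 | 14 | Week 104 |
| Week 108 | 750 | 28 | Week 117 |
| Week 110 | 764 | 42 | Week 117 |
| Week 117 | 813 | 91 | Week 117 |

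**Where a completer's Day 449 value goes.** It is excluded from the Week 64 change summaries (Sections 3.3.2, 3.3.6, 3.3.7) and from the on-treatment TG-over-time summary. It is included in TG over time overall and by age group, in the over-time summaries of other lipids and apoC-III, and in the Section 3.3 table, where Week 64 TG stands for 12-15 months.

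**Month 12, conditional on lipids being drawn at k of Weeks 54, 56 and 58.** The share of the Week 52 value from post-treatment visits is k/(k + 1). The share of Month 12 is half of that if Week 50 is present, and all of it if Week 50 is missing.

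| k | Week 52 | Month 12, Week 50 present | Month 12, Week 50 missing |
|---|---|---|---|
| 0 | 0% | 0% | 0% |
| 1 | 50% | 25% | 50% |
| 2 | 67% | 33% | 67% |
| 3 | 75% | 37.5% | 75% |

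**What the on-treatment repeat removes.** With a last dose on Day 358 the cut is 358 + 28 = Day 386, so Weeks 54 and 56 stay in. With a last dose on Day 351 the cut is Day 379, so Week 54 stays in. Weeks 58 and 65 drop out either way.

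**Earlier boundaries.** Of the 14 upper limits from Week 4 to Week 117, 11 equal the midpoint to the next target within rounding. The exceptions each end 21 days after target:
- Week 13/25: (85 + 169)/2 = 127; stated 106.
- Week 26/38: (176 + 260)/2 = 218; stated 197.
- Week 104/117: (722 + 813)/2 = 767.5; stated 743.

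Day 107 is 22 days from Day 85 and 62 from Day 169, yet it maps to Week 25. Days 107-126 are nearer to Week 13, and Day 127 is equidistant (42 days each way). Likewise Days 198-217 are nearer to Week 26 but map to Week 38. If Week 26 is missing, a Day 107 sample alone supplies Month 6.

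**The case against.** The strongest reply is that the Month 12 effect depends on a schedule not shown here. The SAP does not say that lipids are drawn at Weeks 54, 56 or 58. The Week 117 lipid row supports collection only at the matching 13-week visit, Week 65. The table has no rows for Weeks 106, 108 or 110, the counterparts of Weeks 54 to 58. This stands: a reader might infer that Month 12 does mix on-drug and washout values, and the SAP does not establish that. By the SAP's own 28-day definition, Weeks 54 and 56 also still count as on treatment after a Day 358 last dose.

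A reader might also infer that the Week 64 change-from-baseline results are diluted by completers. They are not, because those summaries are limited to extended-treatment patients. TG over time also has an on-treatment version overall, and the Section 3.3 table shows dose level beside TG, so undosed patients could be recognised there. These safeguards are real, but they do not reach the other lipids, apoC-III or TG by age group.

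Mapping off-treatment landmark values for early discontinuers is a deliberate choice that fits the intention-to-treat character of the FAS. It is not the defect.

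The rule to use only the scheduled visit could be read as meaning only the Week 52 visit. The next sentence, which averages multiple scheduled values, points the other way.

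On the earlier boundaries, the common 21-day limit may be a deliberate cap, and mainly early-termination samples are affected. It is tempting to call a Day 107 value used at Month 6 an imputation, contrary to Section 3.1. It is an observed value placed in a distant window, which is misallocation and not imputation.

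**Conclusion.** The plan leaves a gap that needs a rule. Applied as written, it labels a completer's Week 65 lipid sample, about 13 weeks after the end of treatment, as Week 64 of extended treatment in every over-time summary that is not restricted to extended-treatment patients or on-treatment data. This rests on lipids being drawn at Week 65. The Week 117 row makes that likely, but the SAP does not state it.

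Contamination of Week 52 and Month 12 is conditional on lipids at Weeks 54 to 58; the same holds for Week 104 and Week 106. If such draws exist, the post-treatment share of a completer's Month 12 value is 25% to 37.5% with Week 50 present and 50% to 75% without it. If none exist, it is zero. The number of affected patients cannot be derived from the document.

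The on-treatment repeat is a partial safeguard, planned only for TG change and TG over time. The Week 13 and Week 26 limits misplace samples on 20 study days each, against the stated purpose of the windows.

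The consequences are limited. The study has no primary efficacy endpoint and no formal hypothesis, so what is at risk is the description of how the lipid effect lasts.

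**What to change.** 1. Give fasting lipids from the post-treatment evaluation period their own post-treatment rows, both after Week 52 (Weeks 54-65) and after the extended period (Weeks 106-117). Exclude them from the Week 52, 64 and 104 windows. Assign them by whether the patient has entered post-treatment evaluation, because extended-treatment patients are still being dosed on the same days around Weeks 54-65. Admitting samples up to last dose + 28 days would not be enough: it would still let Week 54, and Week 56 after a Day 358 last dose, into Week 52.
2. Keep the planned landmark mapping for early discontinuers, and say that it applies to them only.
3. Set the Week 13/25 and Week 26/38 boundaries to Days 127 and 218. Leave Week 104/117 where it is: moving it to the midpoint would bring Weeks 108 and 110 (Days 750 and 764) into Week 104.
4. Extend the on-treatment repeat to response rates, other lipids and apoC-III.

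The cost is edits to the window table and its programming. A few values move between visits. No new data are needed.
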